5.2.1.3 Dose Modification for Cisplatin

1. Neutropenia: If on the day of scheduled treatment with cisplatin the absolute neutrophil count (ANC) is $< 1200/\text{mm}^3$, hold the second chemotherapy treatment but not the radiation until $\text{ANC} \geq 1200/\text{mm}^3$, then treat at 100% dose. Neutropenic fever (i.e. any fever $> 38.5^\circ\text{C}$ with an $\text{ANC} < 1000/\text{mm}^3$) will require a 25% dose reduction of the next cisplatin dose. If neutropenic fever occurs with both the first and second dose, cisplatin should be discontinued.
2. Thrombocytopenia: If on the day of scheduled treatment with cisplatin the platelet count is $< 75,000/\text{mm}^3$, hold chemotherapy treatment but not the radiation until platelets are $\geq 75,000/\text{mm}^3$, then treat at 100% dose. Thrombocytopenia that results in bleeding will require a 25% dose reduction of the following cisplatin dose.
3. Neurotoxicity: If grade 2 neurotoxicity develops, hold cisplatin (but continue RT) until toxicity improves to \leq grade 1, then reduce the following cisplatin dose to 80 mg/m^2 . If any signs of grade 3 or greater neurotoxicity occur, discontinue cisplatin, but continue RT.
4. Renal Adverse Events: Cisplatin dose should be based on creatinine clearance immediately prior to the second and third cisplatin dose using the following guidelines:
Note: Creatinine clearance must be calculated (Cockcroft-Gault) in order to make dose adjustment. If the calculated clearance is 50 mL/min or above, a 24-hour urine collection is not needed, but if the calculation is less than 50 mL/min , a 24-hour urine collection is mandated, and the cisplatin dose will be determined as follows:
Creatinine Clearance Cisplatin Dose
 $> 50 \text{ ml}/\text{min}$ then administer 100 mg/m^2
40-50 ml/min then administer 50 mg/m^2
 $< 40 \text{ ml}/\text{min}$ Hold drug*
*Cisplatin should be held (but the RT continued) and the creatinine measured weekly, until creatinine clearance is $> 50 \text{ ml}/\text{min}$, and then the next and following doses of cisplatin should be given at the reduced dose of 50 mg/m^2 .
5. Nausea and Vomiting: Maximum supportive therapy will be given, and cisplatin will be continued at full dose for \leq grade 2 nausea and vomiting. For grade 3 nausea and vomiting refractory to supportive therapy, cisplatin will be held until recovery to $<$ grade 2. No dose reductions will be made.
6. Mucositis: Significant mucositis (grade 3-4, CTCAE, v. 4) is expected from radiation and cisplatin and should not be a reason for a treatment break, unless it significantly interferes with fluid intake or nutrition. Aggressive supportive care is encouraged as well as consideration of a PEG tube if not already done.
7. Ototoxicity: For clinical hearing loss not requiring a hearing aid, reduce cisplatin to 50 mg/m^2 . For hearing loss requiring a hearing aid, discontinue cisplatin. For grade 2-3 tinnitus (CTCAE, v. 4) at the time of retreatment, hold cisplatin until improvement to grade 1 or less and then reduce the following doses of cisplatin to 50 mg/m^2 . If tinnitus does not improve to grade 1 or less by the last day of

radiation therapy, discontinue cisplatin. An audiogram is recommended when there is any report of significant change in hearing and/or an increase in tinnitus.

8. Other Toxicities: For any other grade 3-4 adverse events, hold cisplatin until toxicities have recovered to grade 1 or less.

If the second or third dose of cisplatin is delayed more than 21 days because of hematologic, neurologic, renal, or other adverse events, that dose will be omitted. If a weight change of $\geq 10\%$ occurs, the following cisplatin doses should be adjusted.

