2.1.1.1 Definition of Dose-Limiting Toxicities

All toxicities will be graded using National Cancer Institute (NCI) CTCAE Version 4.0 (see Appendix).

Dose limiting toxicity (DLT) is defined as the appearance of side effects during treatment that are severe enough to prevent continuation of planned treatment. Dose limiting toxicity is defined as grade 3 or 4 non-hematologic toxicities that is definitely, probably, or possibly related to study drug, excluding alopecia, nausea or vomiting, grade 3 tumor flare, rash, mucositis, radiation dermatitis, need for feeding tube, and grade 3 immune-related events that resolve to grade 1 or less within 28 days. However, Grade ≥ 3 immune-mediated adverse events that include pneumonitis, renal failure nephritis, and elevation of AST, ALT, or bilirubin (with an exception for patients with liver metastases with baseline Grade 2 AST or ALT) should result in discontinuation of pembrolizumab and will be considered DLT (please see Table 3 for details on dose modification) .

In addition, adverse effects that are considered secondary to cisplatin or radiation are not considered DLT (see sections 5.2.1.3 and 5.2.2.7) unless they develop after first dose of pembrolizumab and prior to initiation of cisplatin and radiation. Cisplatin or radiation adverse effects include (but are not limited to):

- Grade 3 or 4 renal impairment (with the exception of renal failure or nephritis determined to be immune-related, which will be considered a DLT).
- Grade 2-4 neurotoxicity including ototoxicity (with the exception of myasthenia gravis and Guillain-Barre syndrome, which will be considered a DLT).
- Grade 3 or 4 mucositis
- Grade 3 or 4 myelosuppression

Although the above should result in dose modifications or delays as stated in section 5.2.1.3, they will NOT be considered DLTs for pembrolizumab on this study, and will NOT interfere with expansion to phase II portion of study.

If a patient is taken off study due to the above and has not yet reached evaluation for toxicity attributed to pembrolizumab, that subject will be replaced with another patient on study.

Non hematologic toxicities that will be attributed to pembrolizumab include:

- Grade 3-4 Pneumonitis
- Grade 3-4 diarrhea/colitis
- Grade 3-4 hyperglycemia
- Grade 3-4 hypophysitis
- Grade 3-4 thyroid dysfunction (hypothyroid or hyperthyroid)
- Grade 3-4 hepatic failure (elevation of AST, ALT, Bilirubin)
- Grade 5 toxicity

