5.2.1.4 Timing of Dose Administration

Trial treatment should be administered on Day 1 of each cycle after all procedures/assessments have been completed as detailed on the Trial Flow Chart (Section 6.0). Trial treatment may be administered up to 2 days before or after the scheduled Day 1 of each cycle due to administrative reasons. Day 1 cisplatin and radiation can begin up to 7 days earlier (minimum 14 days after pembrolizumab administration) if patient and /or investigator prefer to expedite initiation of radiation.

All trial treatments will be administered on an outpatient basis.

Initiation of subsequent cycles of pembrolizumab therapy may be delayed for up to 6 weeks to allow recovery from all drug-related toxicity. If the subsequent dose of pembrolizumab is delayed more than 6 weeks because of adverse events, pembrolizumab will be discontinued. Initiation of subsequent cycles of cisplatin therapy may be delayed for up to 3 weeks to allow recovery from all drug-related toxicity. If the subsequent dose of cisplatin is delayed more than 21 days because of adverse events, that dose will be omitted. Alternately, the Investigator may choose to administer supportive care (blood product transfusions) for retreatment criteria to be met. If the recovery criteria are not met after a 6-week delay, the patient will be discontinued from study treatment unless, in the opinion of the Investigator, the patient is experiencing a clinical benefit, in which case a decision regarding continuation of treatment will be made on an individual patient basis in consultation with the Merck medical monitor. Justification will be recorded in the source documents.

In the setting of dose delays, neither cisplatin nor pembrolizumab will be administered following completion of radiation therapy.

When initiating a subsequent cycle, a minimum interval of 21 days should be observed between pembrolizumab administrations and between cisplatin administrations.

Cisplatin or pembrolizumab can be given either before or after the radiation therapy fraction that is given on the same day. If radiation is held for more than 2 days (for any reason), cisplatin may be held as well until radiation resumes.

Note: pembrolizumab or cisplatin given within 48 hours of days 1 and 22 and 43 due to holidays, for example, is acceptable). Weekends count as days. Use the actual body weight for all patients. There should be no dose modifications because of obesity.

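### The cisplatin neutrophil hold in section 5.2.1.3 names only the second treatment, so read literally doses 1 and 3 have no ANC hold

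*Combined protocol and SAP*

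**What the plan says.** Section 5.2.1.3, item 1 sets its trigger without a dose number: "If on the day of scheduled treatment with cisplatin the absolute neutrophil count (ANC) is" below 1200/mm3. The action is narrower: "hold the second chemotherapy treatment but not the radiation until" the ANC is back to at least 1200/mm3, after which the full dose is given. Table 2 (section 5.2) allows at most three cisplatin doses, and the flow chart (section 6.1) places them on days 1, 22 and 43.

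Item 2 of the same section has the same structure for platelets below 75,000/mm3, but no ordinal: "hold chemotherapy treatment but not the radiation until platelets are" at least 75,000/mm3. The closing paragraph provides for omitting a dose: "If the second or third dose of cisplatin is delayed more than 21 days because of hematologic, neurologic, renal, or other adverse events". Section 2.1.1.1 lists "Grade 3 or 4 myelosuppression" among the effects attributed to cisplatin or radiation, and says of that list: "Although the above should result in dose modifications or delays as stated in section 5.2.1.3".

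**The concern.** The trigger applies on every cisplatin day and the action applies to one. Followed to the letter, an ANC of 1100/mm3 stops cisplatin on day 22 but not on day 43. Section 5.2.1.3 uses ordinals deliberately elsewhere: item 4 (renal) and the closing paragraph both name the second and third doses. A careful reader therefore has grounds to take 'second' at face value. A reader who looks at the trigger and at item 2 has equally good grounds to hold any dose.

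At stake is a consistent safety rule for a combination that section 2.1 describes as untested. Section 2.1.1.1 removes grade 3-4 myelosuppression from the dose-limiting toxicities and relies on section 5.2.1.3 to manage it. The run-in observation window (section 2.1.1) closes at the start of the second concurrent cycle, before dose 3. The dose-modification rule is therefore the protocol's specific control for neutropenia at dose 3.

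**Working it through.** This is mainly a check of wording; the plan states no figure to reproduce.

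**Literal coverage of the two haematologic holds**

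| Cisplatin dose | ANC below 1200/mm3 (item 1) | Platelets below 75,000/mm3 (item 2) |
|---|---|---|
| 1 (day 1) | no | yes |
| 2 (day 22) | yes | yes |
| 3 (day 43) | no | yes |

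**Does another section supply the missing ANC figure?**

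- Table 1 (section 5.1.2) requires ANC of at least 1,500/mcL, but for entry only. It is tested within 10 days of starting treatment. Treatment starts with pembrolizumab, planned 14 to 21 days before cisplatin dose 1.
- Item 8 says: "For any other grade 3-4 adverse events, hold cisplatin until toxicities have recovered to grade 1 or less". It covers events not dealt with above it and gives no ANC value.
- Section 5.2.1.4 says: "Initiation of subsequent cycles of cisplatin therapy may be delayed for up to 3 weeks to allow recovery from all drug-related toxicity". This permits a delay but sets no count.
- Section 7.1.3 requires laboratory results to be judged acceptable before each dose, with no threshold.
- The neutropenic-fever rule in item 1 reduces or stops later doses after a febrile episode. It does not cover a low count without fever.

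None of these gives an ANC hold value for dose 1 or dose 3.

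**What a hold at dose 3 means in days**

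Inputs: 35 fractions at five per week, starting on a Monday, Tuesday or Wednesday (sections 5.2 and 5.2.2.1); no cisplatin after radiation ends, and at least 21 days between cisplatin doses (section 5.2.1.4); up to ten treatment days of breaks as the guide maximum (section 5.2.2.6). Day 1 is the first day of radiation, and cisplatin is due on nominal days 1, 22 and 43.

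- Monday start, no breaks: seven full weeks end on the seventh Friday, day 7 × 7 − 2 = 47.
- Tuesday start: 4 + 6 × 5 = 34 fractions in the first seven calendar weeks, and the 35th on the next Monday, day 49.
- Wednesday start: 3 + 6 × 5 = 33 fractions, and the last two on the next Monday and Tuesday, ending on day 49.
- Margin for a hold from day 43: 47 − 43 = 4 days, or 49 − 43 = 6 days.
- With ten missed treatment days, radiation ends 14 days later, on day 61 or 63. The margin is 61 − 43 = 18 or 63 − 43 = 20 days.
- Total cisplatin at full dose: 3 × 100 = 300 mg/m2 if dose 3 is given, 2 × 100 = 200 mg/m2 if it is lost.

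**What a hold at dose 1 would mean, without breaks**

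A hold of d days moves dose 3 to day 43 + d at the earliest, so dose 3 survives only if d is at most 4 to 6. A 7-day hold gives day 50, which is too late. Dose 2 moves to day 22 + d and remains possible while d is at most 47 − 22 = 25, or 49 − 22 = 27.

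**The case against.** The strongest reply is that the literal reading does not work in practice. On day 1 the second treatment is not yet due, and by day 43 it has already been given or omitted, so a sensible clinician would hold the dose due that day. Section 7.1.3 supports this, because results must be acceptable before each dose. A strict reader could also place severe neutropenia at dose 3 under item 8, which would narrow the gap to counts below grade 3. Nor do the neighbouring texts strictly contradict item 1: platelets may have their own rule, and the closing paragraph's haematologic delay of dose 3 could arise from platelets alone. Finally, dose 1 is a weak case, because only pembrolizumab precedes it.

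Much of this stands as a limit on weight. Many clinicians probably would hold. The surrounding text shows intent rather than a formal contradiction, and that evidence is stronger for dose 3 than for dose 1. None of it supplies a number, however. Discretion over what is acceptable is not a common threshold. Item 8 is headed as covering other toxicities and has a different recovery target, so using it for neutropenia adds a third reading. Evident intent is a reason to correct the sentence, not to leave it.

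**Conclusion.** The point holds. Item 1 is wrong as written: two of the three planned cisplatin doses have no literal ANC hold, and nothing else in the protocol fills the gap. Dose 3 is the practical case. There the reading can decide between 300 and 200 mg/m2 if the count is below 1200/mm3 on day 43 and does not recover within 4 to 6 days (18 to 20 days with ten treatment days of breaks). These margins assume cisplatin on the nominal days; the two-day dosing window would shift them slightly. The number of affected patients cannot be estimated from the documents. The sample size and the primary test are unaffected, and so is the section 2.1.2 stopping criterion of at least two cisplatin doses when only dose 3 is held. This is a correction that should be made, not a threat to the trial's conclusions.

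**What to change.** Delete the word 'second' from the action in item 1, so that the hold applies to whichever cisplatin dose is due, as item 2 already does for platelets. The blood count is already scheduled on days 1, 22 and 43, so no test is added.

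The change has three costs:

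- Some patients held on day 43 will lose dose 3. Item 2 already accepts this for platelets.
- A hold at dose 1 starts radiation without cisplatin, again as under item 2. If it lasts more than 4 to 6 days, it also costs dose 3.
- The 21-day omission rule names only doses 2 and 3, so a hold at dose 1 has no stated end. The platelet rule already has this gap.

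Naming the second and third doses instead would avoid the dose-1 consequences. It would still leave dose 1 without an ANC hold, contrary to item 1's own unnumbered trigger and out of line with item 2.

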5.2.1.4 Timing of Dose Administration

Trial treatment should be administered on Day 1 of each cycle after all procedures/assessments have been completed as detailed on the Trial Flow Chart (Section 6.0). Trial treatment may be administered up to 2 days before or after the scheduled Day 1 of each cycle due to administrative reasons. Day 1 cisplatin and radiation can begin up to 7 days earlier (minimum 14 days after pembrolizumab administration) if patient and /or investigator prefer to expedite initiation of radiation.

All trial treatments will be administered on an outpatient basis.

Initiation of subsequent cycles of pembrolizumab therapy may be delayed for up to 6 weeks to allow recovery from all drug-related toxicity. If the subsequent dose of pembrolizumab is delayed more than 6 weeks because of adverse events, pembrolizumab will be discontinued. Initiation of subsequent cycles of cisplatin therapy may be delayed for up to 3 weeks to allow recovery from all drug-related toxicity. If the subsequent dose of cisplatin is delayed more than 21 days because of adverse events, that dose will be omitted. Alternately, the Investigator may choose to administer supportive care (blood product transfusions) for retreatment criteria to be met. If the recovery criteria are not met after a 6-week delay, the patient will be discontinued from study treatment unless, in the opinion of the Investigator, the patient is experiencing a clinical benefit, in which case a decision regarding continuation of treatment will be made on an individual patient basis in consultation with the Merck medical monitor. Justification will be recorded in the source documents.

In the setting of dose delays, neither cisplatin nor pembrolizumab will be administered following completion of radiation therapy.

When initiating a subsequent cycle, a minimum interval of 21 days should be observed between pembrolizumab administrations and between cisplatin administrations.

Cisplatin or pembrolizumab can be given either before or after the radiation therapy fraction that is given on the same day. If radiation is held for more than 2 days (for any reason), cisplatin may be held as well until radiation resumes.

Note: pembrolizumab or cisplatin given within 48 hours of days 1 and 22 and 43 due to holidays, for example, is acceptable). Weekends count as days. Use the actual body weight for all patients. There should be no dose modifications because of obesity.

Pembrolizumab 200 mg will be administered as a 30 minute IV infusion every 3 weeks. Sites should make every effort to target infusion timing to be as close to 30 minutes as

possible. However, given the variability of infusion pumps from site to site, a window of -5 minutes and +10 minutes is permitted (i.e., infusion time is 30 minutes: -5 min/+10 min).

Cisplatin will be given as a bolus, infused over 1-2 hours along with appropriate hydration and anti-emetics.

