5.2.1.2 Dose Modification for Pembrolizumab

Adverse events (both non-serious and serious) associated with pembrolizumab exposure may represent an immunologic etiology. These adverse events may occur shortly after the first dose or several months after the last dose of treatment. Pembrolizumab must be withheld for drug-related toxicities and severe or life-threatening AEs as per Table 3 below. See Section 5.6.1 and Events of Clinical Interest Guidance Document for supportive care guidelines, including use of corticosteroids.

Table 3
Dose Modification Guidelines for Pembrolizumab-Related Adverse Events

Toxicity	Hold Treatment For Grade	Timing for Restarting Treatment	Discontinue Subject
Diarrhea/Colitis	2-3	Toxicity resolves to Grade 0-1.	Toxicity does not resolve within 6 weeks of last dose or inability to reduce corticosteroid to 10 mg or less of prednisone or equivalent per day within 6 weeks.
	4	Permanently discontinue	Permanently discontinue
AST, ALT, or Increased Bilirubin	2	Toxicity resolves to Grade 0-1	Toxicity does not resolve within 6 weeks of last dose.
	3-4	Permanently discontinue (see exception below) ¹	Permanently discontinue
Type 1 diabetes mellitus (if new onset) or Hyperglycemia	T1DM or 3-4	Hold pembrolizumab for new onset Type 1 diabetes mellitus or Grade 3-4 hyperglycemia associated with evidence of beta cell failure.	Resume pembrolizumab when patients are clinically and metabolically stable.
Hypophysitis	2-3	Toxicity resolves to Grade 0-1	Toxicity does not resolve within 6 weeks of last dose or inability to reduce corticosteroid to 10 mg or less of prednisone or equivalent per day within 6 weeks.
	4	Permanently discontinue	Permanently discontinue
Hyperthyroidism	3	Toxicity resolves to Grade 0-1	Toxicity does not resolve within 6 weeks of last dose or inability to reduce corticosteroid to 10 mg or less of prednisone or equivalent per day within 6 weeks.
	4	Permanently discontinue	Permanently discontinue
Hypothyroidism	2-4	Therapy with pembrolizumab can be continued while treatment for the thyroid disorder is instituted	Therapy with pembrolizumab can be continued while treatment for the thyroid disorder is instituted.

Toxicity	Hold Treatment For Grade	Timing for Restarting Treatment	Discontinue Subject
Infusion Reaction	3-4	Permanently discontinue	Permanently discontinue

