Pneumonitis	2	Toxicity resolves to Grade 0-1	Toxicity does not resolve within 6 weeks of last dose or inability to reduce corticosteroid to 10 mg or less of prednisone or equivalent per day within 6 weeks.
	3-4	Permanently discontinue	Permanently discontinue
Renal Failure or Nephritis	2	Toxicity resolves to Grade 0-1	Toxicity does not resolve within 6 weeks of last dose or inability to reduce corticosteroid to 10 mg or less of prednisone or equivalent per day within 6 weeks.
	3-4	Permanently discontinue	Permanently discontinue
All Other Drug-Related Toxicity ²	3 or Severe	Toxicity resolves to Grade 0-1	Toxicity does not resolve within 6 weeks of last dose or inability to reduce corticosteroid to 10 mg or less of prednisone or equivalent per day within 6 weeks.
	4	Permanently discontinue	Permanently discontinue

Note: Permanently discontinue for any severe or Grade 3 drug-related AE that recurs or any life-threatening event.

¹ For patients with liver metastasis who begin treatment with Grade 2 AST or ALT, if AST or ALT increases by greater than or equal to 50% relative to baseline and lasts for at least 1 week then patients should be discontinued.

² Patients with intolerable or persistent Grade 2 drug-related AE may hold study medication at physician discretion. Permanently discontinue study drug for persistent Grade 2 adverse reactions for which treatment with study drug has been held, that do not recover to Grade 0-1 within 6 weeks of the last dose.

Dosing interruptions are permitted in the case of medical / surgical events or logistical reasons not related to study therapy (e.g., elective surgery, unrelated medical events, patient vacation, and/or holidays). Subjects should be placed back on study therapy within 3 weeks of the scheduled interruption, unless otherwise discussed with the Sponsor. The reason for interruption should be documented in the patient's study record.

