5.8 Subject Withdrawal/Discontinuation Criteria

Subjects may withdraw consent at any time for any reason or be dropped from the trial at the discretion of the investigator should any untoward effect occur. In addition, a subject may be withdrawn by the investigator or the Sponsor if enrollment into the trial is inappropriate, the trial plan is violated, or for administrative and/or other safety reasons. Specific details regarding discontinuation or withdrawal are provided in Section 7.1.4 – Other Procedures.

A subject must be discontinued from the trial for any of the following reasons:

- The subject or legal representative (such as a parent or legal guardian) withdraws consent.
- Confirmed radiographic disease progression
Note: For unconfirmed radiographic disease progression, please see Section 5.2.2
- Unacceptable adverse experiences as described in Section 5.2.1.2
- Intercurrent illness that prevents further administration of treatment
- Investigator's decision to withdraw the subject
- The subject has a confirmed positive serum pregnancy test
- Noncompliance with trial treatment or procedure requirements

- The subject is lost to follow-up
- Administrative reasons

The End of Treatment and Follow-up visit procedures are listed in Section 6 (Protocol Flow Chart) and Section 7.1.5 (Visit Requirements). After the end of treatment, each subject will be followed for 30 days for adverse event monitoring (serious adverse events will be collected for 90 days after the end of treatment as described in Section 7.2.3.1). Subjects who discontinue for reasons other than progressive disease will have post-treatment follow-up for disease status until disease progression, initiating a non-study cancer treatment, withdrawing consent or becoming lost to follow-up. After documented disease progression each subject will be followed by telephone for overall survival until death, withdrawal of consent, or the end of the study, whichever occurs first.

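### Table 3 and Section 5.2.1.4 set different limits for stopping pembrolizumab after slowly resolving toxicity if the permitted delay is counted from the due date

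*Combined protocol and SAP*

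**What the plan says.** **Section 5.2.1.2, Table 3.** Seven of the ten toxicity rows set a time limit for recovery: diarrhea/colitis, liver tests, hypophysitis, hyperthyroidism, pneumonitis, renal failure or nephritis, and all other drug-related toxicity. In six of them (all but liver tests) the subject is discontinued on this condition: "Toxicity does not resolve within 6 weeks of last dose or inability to reduce corticosteroid to 10 mg or less of prednisone". The liver row has the 6-week limit without the steroid condition. Footnote 2 applies the same clock to held, persistent grade 2 reactions "that do not recover to Grade 0-1 within 6 weeks of the last dose". The text above the table makes withholding under it obligatory.

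**Section 5.8.** Among the reasons for which a subject must be discontinued is "Unacceptable adverse experiences as described in Section 5.2.1.2".

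**Section 5.2.1.4.** The delay is permitted in these words: "Initiation of subsequent cycles of pembrolizumab therapy may be delayed for up to 6 weeks to allow recovery from all drug-related toxicity". The section then gives its own stopping rule: "If the subsequent dose of pembrolizumab is delayed more than 6 weeks because of adverse events, pembrolizumab will be discontinued". A further sentence deals with failure to recover: "If the recovery criteria are not met after a 6-week delay", the patient leaves study treatment "unless, in the opinion of the Investigator, the patient is experiencing a clinical benefit". In that case continuation is decided individually with the medical monitor. The section also requires at least 21 days between doses of each drug and bars both drugs once radiation is complete. It does not cite Table 3, define the recovery criteria, or say from which date a delay is counted.

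**Section 5.2.1.3.** The cisplatin rule uses the same form of words: "If the second or third dose of cisplatin is delayed more than 21 days" because of adverse events, that dose is omitted.

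**The concern.** Both places use a 6-week limit, but Table 3 starts its clock at the last dose, while 5.2.1.4 appears to start at the date the next dose was due. On a 3-week cycle the second clock runs 3 weeks longer. In that interval one section has already stopped pembrolizumab for good and the other would still let it be given.

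What is at stake is re-exposure after a slow recovery from an immune-related toxicity, during cisplatin and radiation. Section 2.1 says the safety of this combination has not been described before.

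An example on the planned schedule: grade 2 pneumonitis is found on day 1, when dose 2 is due, and clears on day 29, which is 49 days after dose 1. Table 3 called for permanent discontinuation from day 22. Section 5.2.1.4, on the due-date reading, leaves dosing open until day 43. Section 5.6.1 requires a steroid taper of at least 4 weeks once symptoms improve to grade 1 or less. If it starts on day 29 it runs to at least day 57 (29 + 28), so a dose given by day 43 would fall in its first half.

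**Working it through.** **Inputs.** Day 1 is the start of chemoradiation.
- Table 3 limit: 6 weeks = 42 days after the last dose (5.2.1.2).
- Permitted delay: 6 weeks = 42 days (5.2.1.4). Dose interval: 21 days (Table 2; 5.2.1.4).
- Planned doses: dose 1 is 21 days before day 1, then days 1, 22 and 43 (6.1).
- Radiation: 35 fractions, 5 per week, starting on a Monday, Tuesday or Wednesday (Table 2; 5.2.2.1). No pembrolizumab afterwards (5.2.1.4).
- Breaks: ideally no more than 5 treatment days at a time and 10 in total (5.2.2.6).
- Early start: chemoradiation may begin 14 days after dose 1, with dose 2 still 21 days after dose 1 (5.2.1.4; 6.1).

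**Plan's own figure.** 35 / 5 = 7 weeks, as Table 2 states. Counting weekdays, the last fraction is on day 47 (Monday start) or day 49 (Tuesday or Wednesday start). With 5 missed treatment days it is day 54 or 56, and with 10 it is day 61 or 63.

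**Which date starts the delay?** Cisplatin doses must be at least 21 days apart, and a dose is omitted only when delayed more than 21 days. Counted from the last dose, the permitted delay would be 21 - 21 = 0 days and the rule would be empty. For cisplatin the count must therefore run from the due date. The pembrolizumab sentence is worded the same way in the same paragraph.

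**Limits on that reading.** Table 3: last dose + 42. Section 5.2.1.4: last dose + 21 + 42 = last dose + 63 days, or 9 weeks.

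**Excess window** = min(last dose + 63, last fraction) - (last dose + 42), not below 0.

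Planned schedule, unbroken radiation:
- After dose 1: Table 3 closes on day 22 and 5.2.1.4 on day 43. 43 - 22 = **21 days**.
- After dose 2 (day 1): Table 3 closes on day 43; 5.2.1.4 would close on day 64, but radiation ends first. 47 - 43 = 4 to 49 - 43 = 6, so **4-6 days**.
- After dose 3 (day 22): Table 3 closes on day 64, after radiation has ended. **Nil**.

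| Schedule | Missed radiation days | After dose 1 | After dose 2 | After dose 3 |
|---|---|---|---|---|
| Planned | 0 | 21 | 4-6 | 0 |
| Planned | 5 | 21 | 11-13 | 0 |
| Planned | 10 | 21 | 18-20 | 0 |
| Early start | 0 | 18-20 | 0 | 0 |
| Early start | 5 | 21 | 4-6 | 0 |
| Early start | 10 | 21 | 11-13 | 0 |

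For the early start, the Table 3 limits are day 29 (dose 1), day 50 (dose 2, given on day 8) and day 71 (dose 3, given on day 29). The 5.2.1.4 limit after dose 1 is day 50.

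**Effect of the 2-day dosing window.** If dose 2 is given 2 days late, Table 3 closes on day 45 and 47 - 45 = 2. If it is given 2 days early, Table 3 closes on day 41 and 49 - 41 = 8. So 4-6 becomes roughly 2-8 days. If dose 3 is given on day 20 with 10 missed radiation days, the window is 63 - 62 = 1 day, so the zeros after dose 3 mean essentially nil.

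**Doses at stake.** After dose 1 on the planned schedule, at most two: day 23 at the earliest, then 23 + 21 = day 44; the next, day 65, falls after radiation. After dose 2, at most one. In the pneumonitis example with unbroken radiation, only one, since 29 + 21 = day 50 is past the last fraction.

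**Alternative reading.** Counted from the last dose, both limits are last dose + 42 and every window above is zero.

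**The case against.** The strongest reply is that both rules can be obeyed. Table 3 times the resolution of the toxicity, while 5.2.1.4 times the next dose and is permissive. A toxicity that resolves 40 days after the last dose, followed by a dose on day 50 after it, meets both. A patient already stopped under Table 3 has no next cycle to delay, and 5.2.1.2 and 5.8 are mandatory. This stands to the extent that a site applying Table 3 goes wrong nowhere. It does not remove the point, because 5.2.1.4 states its own discontinuation trigger and never defers to Table 3.

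The last-dose reading is also arguable. Six weeks from the last dose is 3 weeks past due, which matches the 3-week cisplatin allowance and the 3-week return limit for interruptions unrelated to therapy in 5.2.1.2. I think the cisplatin wording favors the due date, but the text does not settle it. On the last-dose reading the clinical-benefit exception remains, and the Table 3 rows with the 6-week limit have no counterpart. Its reach is itself unclear: the pembrolizumab stopping sentence just before it is unconditional, and the exception requires consultation with the medical monitor.

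A reader might infer that 5.2.1.4 lets pembrolizumab be given through active toxicity. Its delay rule does not: the delay exists to allow recovery, and Table 3 also requires recovery before restarting. Only the exception contemplates continuing without recovery, case by case. A reader might also infer that 5.2.1.4 requires late dosing or overrides Table 3. The documents support neither.

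**Conclusion.** The two sections give inconsistent limits for a safety stop. On the due-date reading, with nominal dosing days and unbroken radiation from day 1, 5.2.1.4 would permit re-dosing after recovery beyond the Table 3 limit for 21 days after dose 1, about 4-6 days after dose 2 (roughly 2-8 with the 2-day dosing window), and essentially not at all after dose 3. Radiation breaks lengthen the dose 2 window, and an early start with unbroken radiation removes it. On the last-dose reading the clocks agree and only the clinical-benefit exception departs from Table 3.

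The documents give no frequency for such toxicities, so I put no number on the patients affected. It is likely to be few: the toxicity must be held, still be unresolved at 42 days, and then resolve before the later limit. It would be wrong to infer that the trial's results are affected, because no DLT rule, endpoint or analysis depends on this clock. I rate it a minor safety-consistency correction, with moderate confidence because the clock conflict depends on the reading of an undefined delay.

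**What to change.** Amend Section 5.2.1.4 in three respects:
- State that Table 3 governs pembrolizumab: it is permanently discontinued if the Table 3 recovery criteria, including the prednisone condition where the row has one, are not met within 6 weeks of the last dose.
- State that the clinical-benefit exception cannot override a Table 3 discontinuation.
- Keep the bar on dosing after radiation.

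This is the direction 5.8 already points, and it brings every window above to zero on either reading. It is a wording-only amendment with no extra patients or data. The downside is that a few late-recovering patients lose the one or two pembrolizumab doses that 5.2.1.4 might have allowed.
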